#### 6.6.2 Urge to Smoke Data Summarization

Data will be listed by subject, product, and day (and time point as applicable) and summarized by product and visit (and time point as applicable).

Descriptive statistics (number of observations, mean, median, standard deviation, minimum, and maximum) will be used for continuous data variables.

Figures may be used to display the data graphically, as applicable. All data summarizations and figures will be generated using the PK Population. Data summarizations and statistical analyses will be performed using SAS procedures. Statistical analyses are described in Section 6.7.

#### 6.7 Statistical Analyses

# 6.7.1 Statistical Analyses of Primary Endpoints

# Statistical Analyses of Primary BoE (Day 28 only) (*my*bluTM Products Versus the Continue-smoking Arm)

Comparisons of the Day 28 primary BoE (COHb, NNAL, 3-HPMA, and S-PMA) change-from-baseline values between the continue-smoking arm and each *my*bluTM e-liquid product selected at Day 2 will be made using a linear mixed model ANOVA.

The ITT population will be used as the primary analysis population and an analysis using the PP population will be used as a supportive analysis.

The ANOVA model will include product arm, study day, and product arm by study day interaction as fixed effect and subject as a random effect. Least square means (LSMs) will be provided for each product arm at each study day. LSM differences, 95% confidence intervals of LSM differences, and p-values will be provided for the product arm comparisons at each study day. The comparisons of interest will include each of the *my*bluTM product arms compared to continue-smoking arm. The above statistical analyses will be performed using the following SAS codes.

Proc MIXED data=<>; Class subject arm day; Model dependent variable = arm day arm\*day/DDFM=KR; Random Subject; LSMeans arm day arm\*day/pdiff CL alpha=0.05; Run;

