7.1 Sample Size Estimation

This study is prospectively powered to find significant decreases in the primary BoE in subjects who switch to my bluTM e-cigarettes for 28 days.

Exclusive use of blu products during a 5-day in-clinic period was previously shown to reduce the primary BoE to be assessed in this study by $\sim 60\%$ to $\sim 95\%$ (O²Connell et al., 2016). In the same study, reducing cigarette consumption by $\sim 30\%$ of that during the baseline period resulted in $\sim 13\%$ to $\sim 27\%$ reductions. However, no published data are available for the current test products, or similar e-cigarette products, over a longer use period from which a sample size may be estimated for this study. Therefore, the sample size estimation was made using Day 30 data from FDA Center of Tobacco Products Docket # FDA-2017-D-3001 (study ZRHM-REXA-08-US) where the applicant assessed similar BoE in subjects who switched to a tobacco heating product or continued to smoke combustible cigarettes during an out-of-clinic product use period.

Based on this previous data, a minimum of 29 subjects per cohort is estimated to be needed to find differences in the Day 28 S-PMA change-from-baseline value equivalent to a 50% reduction in biomarker value compared to the continue-smoking arm using one-sided significance level of 0.0125 (alpha of 0.05 adjusted for multiple comparisons using the Bonferroni method) with a power of at least 80%. Approximately 43 subjects are planned to be randomized into each *my*bluTM e-liquid cohort and 40 subjects into the continue-smoking arm to better ensure that the minimum number complete the Day 28 assessments. The following table provides the power estimate for each of the primary endpoint biomarkers assuming 29 subjects in the ITT population complete the study.

	Test group	Test group	Control group	
	baseline	change-from-baseline	change-from-baseline	
Biomarker	value	SD	SD	Power
COHb (% sat)	6.95	2.28	1.73	>0.9999
NNAL (ng)	340	178	133	0.9623
3-HPMA (µg)	1325	494	500	0.9968
S-PMA (ng)	3348	2370	1512	0.8106

The baseline and change-from-baseline SD values in this table were derived from study ZRHM-REXA-08-US in US FDA Center of Tobacco Products Docket # FDA-2017-D-3001 who had reported Baseline and Day 30 measurements for the listed biomarkers.

Abbreviations: 3-HPMA = 3-hydroxypropylmercapturic acid, COHb = carboxyhemoglobin, NNAL = 4-(methylnitrosamino)-1-(3-pyridyl)-1-butanol, SD = standard deviation, S-PMA = S-phenyl mercapturic acid.

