# Statistical Analyses of Pharmacokinetics (*my*bluTM Products Versus the Continuesmoking arm or JUUL arm)

A linear mixed model ANOVA will be performed on the log-transformed nicotine PK parameters AUC and Cmax from each product use session (PK population). The model will include product arm as a fixed effect. Geometric LSMs will be provided for the PK parameters of Cmax and AUC by product arm. Geometric LSM ratio, 95% confidence intervals of geometric LSM ratio, and p-values will be provided for the product arm comparisons for Cmax and AUC. The comparisons of interest will include each of the *my*bluTM product arms compared to continue-smoking arm or JUUL arm. The above statistical analyses will be performed using the following SAS codes.

```
Proc MIXED data=<>;
Class subject arm;
Model LN_dependent variable = arm/DDFM=KR;
LSMeans arm/pdiff CL alpha=0.05;
Run;
```

Non-parametric analysis (Wilcoxon Rank Sum test) will be performed for the comparisons of  $T_{max}$  between test and reference products.

Similar methods will be used to compare the urge to smoke parameters.

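### The SAP's primary model gives all five arms one variance, but the trial was sized on unequal variances; if the planning SDs hold, S-PMA power at the 29-per-arm minimum is about 0.75, not 0.81

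*SAP*

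**What the plan says.** SAP 6.7.1 analyses Day 28 change from baseline in the four primary biomarkers with a linear mixed model containing arm, day and "product arm by study day interaction as fixed effect and subject as a random effect". The SAS code has `Random Subject` with `DDFM=KR`. It has no `REPEATED` statement and no `GROUP=` option, so one subject variance and one residual variance serve all five product arms. Contrasts are requested with "pdiff CL alpha=0.05".

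Protocol 7.1 gives the basis of the sample size: "minimum of 29 subjects per cohort is estimated to be needed to find differences in the Day 28 S-PMA change-from-baseline value". The difference to be detected is half of the baseline value. The level is set as "one-sided significance level of 0.0125 (alpha of 0.05 adjusted for multiple comparisons using the Bonferroni method"), and the power target is 80% or more. Its table gives separate change-from-baseline SDs for test and control. The row that sets the sample size reads "S-PMA (ng) 3348 2370 1512 0.8106": baseline, test SD, control SD, power.

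SAP section 8 says its analyses are aligned with the protocol's. For pharmacokinetics, SAP 6.7.2 says "The model will include product arm as a fixed effect", again with no arm-specific variance.

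**The concern.** The sample size assumes one test and the SAP specifies another. In a balanced two-arm comparison, pooling unequal variances does little harm, because the average of the two variances gives the correct SE. Here the common variance is averaged over five arms, and four of them would carry the larger test-group SD. The pooled figure is therefore pulled towards the test-group SD. It is too large for a contrast with continue-smoking and too small for a contrast between two e-liquids.

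At stake are the width of the primary intervals for three biomarkers, the promised 80% power for S-PMA at the stated minimum, and the coverage of the between-e-liquid intervals (Protocol 7.5.2; SAP Tables 14.2.2.1.4.1 and 14.2.2.1.4.2). Larger spread in the myblu cohorts is plausible in this trial. The ITT population ignores compliance (Protocol 7.2.2), and smoking by myblu subjects in ambulatory periods is not recorded as a deviation (Protocol 4.3.3), so full switchers and dual users can be mixed.

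**Working it through.** **Inputs (Protocol 7.1).** Effect Δ = 50% of test-group baseline; one-sided α = 0.0125; n = 29 per arm. Baseline, test SD and control SD are: S-PMA 3348, 2370, 1512; NNAL 340, 178, 133; 3-HPMA 1325, 494, 500; COHb 6.95, 2.28, 1.73.

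**1. Reproduce the stated power.** For S-PMA, Δ = 0.5 × 3348 = 1674.
- SE = √((2370² + 1512²)/29) = √(7,903,044/29) = 522.0.
- Noncentrality = 1674/522.0 = 3.207.
- Satterthwaite df = 28 × (2370² + 1512²)² / (2370⁴ + 1512⁴) = 47.6.
- Noncentral-t power = 0.8106, as stated.

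The same method gives NNAL 0.9623, 3-HPMA 0.9967 (stated 0.9968) and COHb >0.9999. A two-arm pooled t test gives 0.8140 for S-PMA and 0.9629 for NNAL. A normal approximation gives 0.8328 for S-PMA. Neither matches, so the protocol used an unequal-variance t test.

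**2. SE under the SAP model.** Assume every myblu cohort has the test-group SD and the Day 56 SD equals the Day 28 SD.
- Common variance = (4 × 2370² + 1512²)/5 = 24,753,744/5 = 4,950,749, so SD = 2225.
- Model SE = 2225 × √(2/29) = 584.3, with df = 5 × 28 = 140.
- Ratio to the true SE = 584.3/522.0 = 1.12.

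| Biomarker | True SE | Pooled SE | Ratio | Stated power | Power, pooled model |
|---|---|---|---|---|---|
| S-PMA | 522.0 | 584.3 | 1.12 | 0.8106 | 0.75 |
| NNAL | 41.3 | 44.6 | 1.08 | 0.9623 | 0.95 |
| COHb | 0.531 | 0.573 | 1.08 | >0.9999 | >0.999 |
| 3-HPMA | 130.5 | 130.0 | 1.00 | 0.9968 | 0.997 |

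**3. S-PMA power.** Power = Φ((Δ − t × pooled SE)/true SE).
- One-sided 0.0125: t = 2.266, so the difference must exceed 2.266 × 584.3 = 1323.9. Power = Φ((1674 − 1323.9)/522.0) = Φ(0.671) = 0.749. Simulation of 200,000 trials gives 0.747.
- The SAP's coded level (two-sided 0.05): t = 1.977, threshold 1155.2. Power = Φ(0.994) = 0.84.
- One-sided 0.0125 with 43 per myblu cohort and 40 controls: 0.90, against 0.94 with unequal variances.
- One-sided 0.0125 at 32 per arm: 0.798; at 33: about 0.81. So 33 per arm are needed for 80%.

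**4. S-PMA error rate and coverage at 29 per arm.**
- One-sided error of a nominal 0.0125 test: 1 − Φ(2.266 × 1.119) = 0.0056 (about 0.006 simulated).
- 95% CI coverage, myblu versus control: 2Φ(1.977 × 1.119) − 1 = 0.973 (0.972 simulated).
- 95% CI coverage, e-liquid versus e-liquid: 2Φ(1.977 × 2225/2370) − 1 = 0.937 (0.935 simulated).

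**5. Two variance groups instead.** Pool the four myblu cohorts and keep continue-smoking separate. The SE returns to 522.0 with df = (2370² + 1512²)² / (2370⁴/112 + 1512⁴/28) = 133. Noncentral-t power at one-sided 0.0125 is 0.825, so the promised 80% is met at 29 per arm.

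**The case against.** The strongest reply is that the primary error is on the safe side: a nominal 0.0125 test runs near 0.006, so no false claim of reduced exposure becomes more likely. That stands. A reader might infer that the primary inference is invalid, but the figures show lost efficiency and over-wide intervals, not inflated false positives against control.

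A reader might also take 0.75 as the trial's S-PMA power. The documents do not support that. The figure combines the protocol's alpha with the SAP's model, and the SAP codes 0.05, where power is 0.84. It also needs exactly 29 completers, which Protocol 7.1 calls a minimum; 33 per arm lies within the planned 43 and 40. And it needs an effect of only 50%: at 60% the pooled model gives 0.90 even at 29 per arm and 0.0125. These limits stand. The 0.84 does not settle the matter, however, because it is reached only by leaving the Bonferroni level on which the trial was sized, and that mismatch is a separate question.

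The SDs are borrowed from a tobacco heating product study, and Protocol 7.1 says no published data exist for these products over a longer use period. One test-group SD for all four cohorts and an equal SD on Day 56 are assumptions. The SE errors are therefore conditional.

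A reader might extend the point to all four biomarkers, or put a figure on it for pharmacokinetics. 3-HPMA is unaffected (494 against 500). The only pharmacokinetic variability in the documents comes from a 15-subject crossover with AUC over 30 minutes, no Honeymoon flavor and no JUUL arm, so the size there cannot be established.

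**Conclusion.** The mismatch is real. The SAP's pooled five-arm variance does not deliver the power that Protocol 7.1 states, although SAP section 8 claims alignment. The consequence is moderate: wider-than-needed primary intervals for S-PMA, NNAL and COHb, mild under-coverage between e-liquids, and an S-PMA shortfall of about 0.06 at the minimum sample size and the protocol's alpha. No other primary biomarker falls below 80% power. All these sizes depend on the planning SDs holding in every myblu cohort and on both days.

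**What to change.** In SAP 6.7.1, pre-specify two variance groups: the four myblu cohorts together, and continue-smoking. One way is to replace `Random Subject` with `Repeated day / subject=subject type=cs group=grp`, where `grp` is a myblu/control indicator added to the CLASS statement, and to keep `DDFM=KR`. The fixed effects and contrasts stay as they are. The sentence describing subject as a random effect must change, and SAP 6.7.2 should say whether the same structure applies to the secondary endpoints that follow this approach.

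The cost is small: four covariance parameters instead of two, and slightly fewer error df (about 133 against 140 in the single-day calculation). An unstructured covariance for each of the five arms would need 5 × 3 = 15 parameters and probably a data-driven fallback for non-convergence, which two groups make unnecessary.

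If the pooled model is kept, restate Protocol 7.1: S-PMA power is about 0.75 at 29 per arm and one-sided 0.0125, and 33 per arm are needed for 80%. Arm-specific variance in the pharmacokinetic model is optional.

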Statistical Analysis	Comparisons of the Day 28 visit primary BoE change-from-baseline values between the continue-smoking arm and each my blu TM e-liquid product selected at Day 2 will be made using a linear mixed model analysis of variance (ANOVA). The intent-to-treat (ITT) population will be used as the primary analysis population and an analysis using the per-protocol (PP) population will be used as a supportive analysis.
	An approach similar to that used for the primary endpoints will be used to make Day 28 and Day 56 change-from-baseline comparisons for the applicable secondary endpoints. For the Day 56 analysis, the initial my blu [™] e-liquid cohort assignments for each subject will be maintained within the statistical model and a separate sensitivity analysis will be performed for subjects that do not switch flavors at Day 29.

	Comparisons of the primary and secondary BoE change-from-baseline values at each time point within and between the four my blu TM e-liquid flavor product cohorts will also be made using a linear mixed model ANOVA.
	A linear mixed model ANOVA will be performed on the log-transformed nicotine AUC and C_{max} PK parameters from each product use session. Non-parametric analysis (Wilcoxon Signed Rank test) will be performed for the comparisons of Tmax. Similar models will be used to compare the urge to smoke parameters. The comparisons of interest will include each of the my blu TM products compared to the usual brand cigarette and JUUL [®] product.
Safety Assessments	Screening safety evaluations will include a physical examination, vital signs, electrocardiogram (ECG), clinical laboratory tests (clinical chemistry, hematology, urinalysis, and serology), lung function, follicle-stimulating hormone (FSH) test (post-menopausal females), and serum and urine pregnancy tests (females only).
	On-study evaluations will include a symptom-driven physical examination, vital signs, ECG, clinical laboratory tests (clinical chemistry, hematology, and urinalysis), lung function, and urine pregnancy tests (females only).
	AEs spontaneously reported by the subjects or observed by the Investigator or other study personnel will be documented and monitored from the time of first product use after successful completion of the check-in events for Test Visit 1 through the end of the Follow-up Period. Any prior and concomitant medications taken from 30 days prior to Screening through the Follow-up Period will also be recorded.

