2.2 Study Hypothesis

The study hypothesis is that switching from usual brand combustible cigarettes to a mybluTM e-cigarette will result in a significantly larger decrease from baseline in the primary tobacco-related biomarkers following 28 days of use relative to the change associated with continuing to smoke combustible cigarettes. The following hypothesis will be tested independently for each mybluTM e-liquid.
H₀: $\Delta \mu_{\text{test}} = \Delta \mu_{\text{cont}}$

 $H_A: \Delta \mu_{test} > \Delta \mu_{cont}$

Where H₀ is the null hypothesis, H_A is the alternative hypothesis, $\Delta \mu$ = the mean decrease from baseline, "test" = *my*bluTM product, and "cont" = combustible cigarette

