7.5 Statistical Analysis

7.5.1 Primary Endpoints

Comparisons of the Day 28 visit primary BoE change-from-baseline values between the continue-smoking arm and each mybluTM e-liquid product selected at Day 1 will be made using a linear mixed model ANOVA. The ITT population will be used as the primary analysis population and an analysis using the PP population will be used as a supportive analysis.

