# 2.2 Endpoints

# **Hypothesis:**

Switching from usual brand combustible cigarettes to a *my*bluTM e-cigarette will result in a significant decrease from baseline in the primary tobacco-related BoE following 28 days of use relative to the change associated with continuing to smoke combustible cigarettes. The hypothesis will be tested independently for each *my*bluTM e-liquid Product.

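### The one-sided 0.0125 level that sized the trial is not carried into the primary analysis, and neither document states a decision threshold, a test family or a success rule

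*SAP*

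**What the plan says.** **Sizing.** Protocol 7.1 finds a minimum of 29 subjects per cohort for S-PMA at a "one-sided significance level of 0.0125 (alpha of 0.05 adjusted for multiple comparisons using the Bonferroni method) with a power of at least 80" percent. The adjusted level is 0.05/4, but the section does not say which four comparisons are meant.

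**Hypothesis.** Protocol 2.2 is directional: it expects a "significantly larger decrease from baseline in the primary tobacco-related biomarkers following 28 days of use" than under continued smoking, and its alternative is one-sided. It adds "The following hypothesis will be tested independently for each" e-liquid. The hypothesis in SAP 2.2 has the matching sentence, "The hypothesis will be tested independently for each" e-liquid. Neither gives a level or says how the four primary biomarkers combine.

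**Analysis.** Protocol 7.5.1 specifies a "linear mixed model ANOVA. The ITT population will be used as the primary analysis population", with per-protocol as supportive. The synopsis says the same ("The intent-to-treat (ITT) population will be used as the primary analysis population"). Neither gives alpha, sidedness or a family. SAP 6.7.1 keeps the model and populations and promises that "LSM differences, 95% confidence intervals of LSM differences, and p-values will be provided for the product arm comparisons at each study day". Its LSMEANS statement uses "pdiff CL alpha=0.05" with no multiplicity option. The ITT and per-protocol comparison shells in SAP 10.2 (Tables 14.2.2.1.2.1 and 14.2.2.1.2.2) show a 95% interval and one p-value for each of four products at each day, with no significance criterion.

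**The concern.** The primary hypothesis is confirmatory and directional, and the trial was sized on a specific adjusted level. A reader who goes to the analysis sections to learn what counts as a positive result finds no answer. Three things are missing:

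- the threshold that a p-value must meet;
- the family over which 0.05 was split, since a divisor of 4 fits four e-liquids or four biomarkers equally well while 4 × 4 = 16 Day 28 contrasts are planned;
- whether an e-liquid succeeds on any one primary biomarker or only on all four.

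The only interval the SAP specifies is a 95% two-sided one. Its natural companion is a two-sided 0.05 test, which in the favourable direction is one-sided 0.025. A report could present intervals that exclude zero as significant while missing the level used to size the trial. At stake are the false-positive rate of the primary claim and the agreement between the stated power and the test actually applied.

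**Working it through.** **Inputs** (Protocol 7.1): n = 29 per group; effect = 50% of test-group baseline; one-sided alpha 0.0125 = 0.05/4. S-PMA baseline is 3348 ng, with change-from-baseline SDs of 2370 (test) and 1512 (control).

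**1. Reproduce the stated power for S-PMA** (two-group t-test, unequal variances, noncentral t).

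- Difference = 0.5 × 3348 = 1674 ng.
- SE = √(2370²/29 + 1512²/29) = √(193,686 + 78,833) = 522.0.
- Noncentrality = 1674/522.0 = 3.207; Satterthwaite df = 47.6.
- Critical t at one-sided 0.0125 = 2.315, giving power **0.8106**, exactly as stated.

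The same method gives COHb >0.9999, NNAL 0.9623 and 3-HPMA 0.9967 (stated: >0.9999, 0.9623, 0.9968). For S-PMA, n = 28 gives 0.7946, so 29 is the smallest n that reaches 80%. The sizing is sound and rests on 0.0125.

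**2. The level implied by the SAP outputs if read conventionally.** Two-sided p < 0.05 with the difference in the favourable direction is one-sided 0.025, or 2 × 0.0125. Critical t falls to 2.011 and S-PMA power becomes **0.8813**.

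**3. Family-wise error, all nulls true, under each reading of the divisor.**

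| Family of four | One-sided 0.025 | One-sided 0.0125 |
|---|---|---|
| Four e-liquids against one shared control, one biomarker, equal SDs, 29 per group (correlation 0.5) | 7.8% | 4.1% |
| Four biomarkers within one e-liquid, any one sufficient, correlation 0.8 to 0 | 5.7–9.6% | 3.0–4.9% |
| Upper bound for any four tests (4 × alpha) | 10% | 5% |

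The first two rows are simulated. For independent tests the formula is 1 − (1 − alpha)⁴: 1 − 0.975⁴ = 9.6% and 1 − 0.9875⁴ = 4.9%, which are the upper ends of the second row. The 0.5 follows from equal variances and equal group sizes. The between-biomarker correlations are assumptions, because the documents give none.

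**4. Interval width at the sizing level.** A two-sided 97.5% interval matches one-sided 0.0125. Its width relative to a 95% interval is 2.315/2.011 = 1.15 at 47.6 df, and 1.14 in the normal limit.

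**5. What the success rule does to power.** If all four biomarkers must succeed at 0.0125, the stated powers bound the joint power per e-liquid. It is at least 1 − (0.1894 + 0.0377 + 0.0032 + 0.0001) = 0.77 and at most 0.8106. Under independence it is 0.8106 × 0.9623 × 0.9968 = 0.78.

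**The case against.** The strongest reply is that the level has been specified. Protocol 7.1 sits inside the data analysis section and gives level, sidedness and method. The opening of Protocol 7 requires major modifications of the primary analysis to go through a protocol amendment. Raw p-values are printed, so 0.0125 can be applied directly, and Bonferroni needs no option in the code. This stands in part. Nothing in the SAP prevents use of 0.0125, and a laxer level adopted through the SAP alone would be hard to defend. But a level stated only as a sizing assumption is not a decision rule, and the family and success rule are stated nowhere.

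A second reply is that testing each e-liquid independently makes each one its own claim, so the divisor covers biomarkers. That is a coherent reading, and the second row of the table then applies instead of the first. The text does not establish it, and it still leaves any-or-all open.

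Several stronger readings are tempting but not supported:

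- **The SAP relaxed the protocol's level to 0.05.** The `alpha=0.05` option sets only the interval level, no passage adopts 0.05 as a threshold, and Protocol 7.5.1 is equally silent. For the same reason the alignment statement in SAP 8 is defensible: the SAP mirrors 7.5.1.
- **Error runs over all 16 contrasts.** That matters only if any single biomarker on any e-liquid would support one overall claim, which the plan does not say.
- **The stated power is wrong.** It reproduces exactly.
- **Different verdicts at the two thresholds under a true 50% effect show false claims.** With a real effect, the laxer threshold gives the right answer. Such differences describe power, not error.

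**Conclusion.** The point holds as an omission shared by the two documents. The level behind the sample size is not stated in the primary analysis, the specified 95% interval does not match it, and the family and success rule are undefined. If the outputs are read at two-sided 0.05, the per-test level doubles. Family-wise error rises from about 4.1% to 7.8% over four e-liquids, or from about 3.0–4.9% to 5.7–9.6% over four biomarkers within an e-liquid, and the stated S-PMA power of 0.81 no longer describes the test (0.88). The error figures assume normal test statistics and, respectively, equal SDs with one shared control and assumed correlations of 0.8 to 0. The power figures assume the planning SDs, which come from a different product.

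This should be fixed, but it does not undermine the design. The printed p-values allow 0.0125 to be applied, three of the four biomarkers have stated power above 0.96, and no data are lost.

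**What to change.** Add to SAP 6.7.1 and Protocol 7.5.1:

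1. **Level and direction.** Test each Day 28 ITT primary contrast at one-sided 0.0125, that is two-sided p < 0.025 with the LS mean difference (Test − Reference) below zero. Show a matching two-sided 97.5% interval (`alpha=0.025`) in place of the 95% interval or beside it, and adjust the shell headers for these contrasts. Keeping the 95% interval for estimation is acceptable if the decision interval is labelled.
2. **Family.** State which four comparisons the divisor covers: four e-liquids within a biomarker, or four biomarkers within an e-liquid.
3. **Success rule.** State whether an e-liquid succeeds on all four primary biomarkers or on any one. If all four are required, no further adjustment across biomarkers is needed, but joint power per e-liquid at 29 completers is about 0.77–0.81.

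The cost is a few sentences in each document, one SAS option and the headers, with no new subjects or data. The intervals used for the decision become about 15% wider. The minimum of 29 per cohort and the stated power of 0.8106 are unchanged, since both were derived at 0.0125.
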